#### 2.2.4 Current UK recommendations

In 2000, [name] and [name] at St Mark's Hospital were invited to undertake a review of the literature and to develop guidelines for the colonoscopic surveillance following adenoma detection (see figure below). We identified a low-risk group for which it was suggested that colonoscopic surveillance might not be necessary and a high-risk group for which surveillance is definitely indicated, at least 3 yearly and maybe more frequently initially. This latter group includes people with 5 or more adenomas or 3-4 adenomas at least one of which is advanced; this group comprises only around 5% of people with adenomas. This left an intermediate risk group for which there is no evidence to indicate that it is safe not to offer surveillance. The available evidence suggested that it might be safe to stop surveillance after two negative exams, depending on the age of the patient and the quality of the examinations. However, it is possible that patients with intermediate adenomas are a heterogeneous group with respect to their risk of developing CRC and that longer intervals might suffice for a subgroup. It is also possible that it is not necessary to have two negative exam might be sufficient.

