# 2.3.1 Analysis of risk of cancer or advanced adenomas with varying frequency of colonoscopy surveillance

The aim of the statistical analysis is to answer the following questions:

- 1. Is there substantial heterogeneity of results at subsequent examination in terms of detection rates of advanced adenomas or CRC according to baseline characteristics and interval to first follow-up colonoscopy?
- 2. If so, is there a subgroup that does not need subsequent examination identifiable at baseline, and is the magnitude of this subgroup meaningful?
- 3. For those who do need follow-up can we identify a group for whom an interval of 3 years is too long? Similarly is there a group for whom 3 years is too short?
- 4. For the latter group, how long can the interval safely be extended to?
- 5. Is there a subgroup who needs a second examination but no further follow-up thereafter, and if so, how is the group identified from the baseline and first follow-up examination results?
- 6. What is the risk of CRC in each adenoma risk-group defined according to current UKadenoma surveillance guidelines:
  - a) What is the long-term CRC risk in those who have no surveillance?
  - b) What is the long-term CRC risk in those who do have at least one, or two or more surveillance exam(s)?
  - c) Are there sub-groups in which CRC risk is low enough not to warrant surveillance?
  - d) Among those whose risk is determined high enough to require surveillance, when would CRC risk become sufficiently low to safely stop surveillance?
- 7. Should risk-groups be redefined based on long-term CRC risk such that some patients might be reclassified as lower risk?
- 8. What are appropriate surveillance intervals within defined risk groups to warrant colonoscopy but not result in unacceptably high interval cancers?

9. What are the health and economic impacts of refined risk groups and surveillance intervals?

For questions 1-4 the analysis will draw on data on the baseline examination and the first follow-up examination, in particular how the findings at the latter relate to those at the former. For question 5, we will relate the findings at second and subsequent follow-up examinations to those at baseline and first follow-up examination.

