The statistical analysis strategy will be split into three stages: (1) analysis of first follow-up findings in relation to baseline findings; (2) analysis of second and subsequent follow-up findings in relation to baseline and first follow-up findings, and (3) analysis of rates of symptomatic CRC in the years after final endoscopic examination.

Analyses will be performed both including and excluding those with first follow-up less than 3 years after baseline, as this may be a reflection of clinical opinion of extra high risk. Results of all analyses will be confirmed by internal cross-validation.

For questions 6 – 8 our statistical analyses will focus on the long-term CRC incidence after

baseline. To assess the effect of surveillance on CRC risk, we will compare the incidence of CRC both in the absence and presence of surveillance, and compare CRC risk with that expected in the general population. Cox proportional hazard models will be used to assess the relationship between baseline characteristics and CRC risk to identify subgroups in which CRC risk is low enough to justify less intensive surveillance and reclassification of risk. In those who benefit from surveillance, the CRC risk will be examined after multiple exams to estimate when surveillance could safely stop, or multiple intervals to estimate the appropriate interval length between surveillance exams.

Additional health economic analyses will be conducted to estimate the cost implications of alternative surveillance strategies (question 9).

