#### 2.9.2 Second and subsequent follow-up

Analysis of findings at second and subsequent follow-up will closely parallel those of first follow-up with the slight complication of the need to consider their joint association with both baseline and first follow-up results. As for part (a) of the analytic strategy, simple analysis of rates of polyps by time since last examination, the major difference will be stratification by the two previous examinations.

For part (b), the logistic regression, the endpoint (y-) variable will be the finding at second or subsequent follow-up and the x-variables studied will be firstly as before the time since last examination and baseline. Then we will augment the model with findings at first follow-up examination to see if these significantly improve prediction of findings at second and subsequent follow-up. The logistic regression model would now be

where  $x_1$  represents time since last examination,  $x_2$  size of polyp at last examination,  $x_3$  multiplicity of polyps at last examination,  $x_4$  presence of polyps at first follow-up examination etc.

The formal multistate modelling in (c) will be carried out to model sensitivity, incidence and

progression after the first follow-up. The results will give a further indication of the desirability or otherwise of subsequent follow-up beyond the first one and of changing the frequency of examination after the first follow-up.

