### 2.9.3 Analysis of colorectal cancer occurrence after endoscopic examination

The analyses above will be complemented by analyses of subsequent clinical CRCs in the follow-up period where available. Such events are rare and estimates will therefore be imprecise, but the analysis will add some value to the exercise, by enabling us to assess the trade-off between harvest of polyps at subsequent examination and expected number of cancers occurring before the subsequent examination. Again the analysis will proceed in steps of increasing complexity, beginning with simple description of rates of cancers by time since and findings at last examination, through regression modelling to formal multistate models.

We will assess the absolute risk of CRC using Kaplan-Meier curves and will compare the incidence of CRC to that expected in the general population, both in the absence and in the presence of surveillance. We will use Cox proportional hazards models to assess the effect of surveillance on the risk of CRC, with the number of follow-up visits included as a time-varying covariate.

The models will also be used to assess the relationship between patient, polyp and procedural characteristics at baseline and CRC risk. We will use univariable models to estimate unadjusted hazard ratios and will use multivariable models to estimate the effect of surveillance adjusted for patient, polyp and procedural characteristics and to identify independent predictors of future CRC risk. The risk factors identified in the multivariable models will then be used to aid in the creation of distinct subgroups. These subgroups will then be scrutinised to determine whether in any subgroup the CRC risk after baseline is low enough relative to the general population to not warrant surveillance. Conversely, in subgroups that do appear to benefit from surveillance, the results will be examined to see whether the risk of CRC becomes low enough after a certain number of exams in order for surveillance to safely cease.

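### The stopping analysis for colorectal cancer counts exams within baseline subgroups and is not linked to what the surveillance exams found

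*Combined protocol and SAP*

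**What the plan says.** Question 6d (section 2.3.1, repeated in Appendix 1.0 part b) asks when, among patients who need surveillance, CRC risk falls far enough for it to stop. Two places say how this will be answered.

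- Section 2.3.1, methods for questions 6–8: "the CRC risk will be examined after multiple exams to estimate when surveillance could safely stop".
- Section 2.9.3: in subgroups that appear to benefit from surveillance, the results will show "whether the risk of CRC becomes low enough after a certain number of exams in order for surveillance to safely cease".

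The supporting Cox model represents surveillance "with the number of follow-up visits included as a time-varying covariate". The risk factors used to form the subgroups come from the "relationship between patient, polyp and procedural characteristics at baseline and CRC risk".

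Three other passages do look at what follow-up exams found.

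- Section 2.9.3 opens with a "simple description of rates of cancers by time since and findings at last examination", then moves to regression and multistate models.
- Question 5 seeks patients who need one further exam and no more, and asks "how is the group identified from the baseline and first follow-up examination results".
- Section 2.9.2 will "augment the model with findings at first follow-up examination to see if these significantly improve prediction" of findings at later exams.

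The background in section 2.2.4 reports that it "might be safe to stop surveillance after two negative exams", subject to age and exam quality.

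**The concern.** Followed as written, the stopping step gives one answer per baseline subgroup and exam count. Take two patients in the same baseline subgroup, one with two clear exams and one with large adenomas at both. They have the same visit count and the same baseline covariates, so they receive the same stopping answer.

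The error matters most in one direction. If the pooled CRC risk after a given number of exams looks low enough, the conclusion to stop extends to the minority with advanced surveillance findings, whose risk may be several times higher. The subgroups do not prevent this, because they are fixed at baseline and cannot separate patients by what surveillance found later.

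This concerns which risk is estimated for question 6d. It is separate from whether the surveillance effect is adequately adjusted for confounding.

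**Working it through.** **Step 1: follow exam findings through the plan.**

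| Analysis | Outcome | Are surveillance findings used? |
|---|---|---|
| 2.9.3, opening description | CRC | Yes, findings at last exam |
| 2.9.3, Cox model | CRC | Not stated: visit count plus baseline characteristics |
| 2.9.3 and 2.3.1, stopping step (6d) | CRC | Not stated: exam count within subgroups |
| 2.9.2, rates and logistic regression | Adenoma findings at later exams | Yes |
| 2.9.2, multistate step | Sensitivity, incidence, progression after first follow-up | Not stated |

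The one CRC analysis that explicitly uses surveillance findings is the opening description. No sentence links it to the stopping step.

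**Step 2: illustrate the size.** The plan gives no figure to reproduce here. The inputs are borrowed from its background:

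- Share *f* with advanced findings at follow-up: 3% (US National Polyp Study, sections 2.2.2 and 2.2.3), and 5.2% and 8.6% (advanced neoplasia at two and four years in the Funen study, section 2.2.3). Section 2.8 also anticipates 3% with intermediate- or high-risk lesions at second or later follow-up.
- Relative risk *R*: 3 and 5 (section 2.2.2). These describe baseline adenomas compared with the general population. Using them for surveillance findings, relative to patients without such findings, is an assumption.

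Let *c* be the ratio to the general population in patients without advanced findings, and let the pooled ratio be 1.0. Then (1 − f)c + fRc = 1, so c = 1/[(1 − f) + fR]. The ratio with advanced findings is Rc, and their share of later CRCs is fRc.

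| f | R | Without: c | With: Rc | Share of CRCs |
|---|---|---|---|---|
| 3% | 3 | 1/1.06 = 0.94 | 2.83 | 8% |
| 3% | 5 | 1/1.12 = 0.89 | 4.46 | 13% |
| 5.2% | 3 | 1/1.104 = 0.91 | 2.72 | 14% |
| 5.2% | 5 | 1/1.208 = 0.83 | 4.14 | 22% |
| 8.6% | 3 | 1/1.172 = 0.85 | 2.56 | 22% |
| 8.6% | 5 | 1/1.344 = 0.74 | 3.72 | 32% |

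The ratio is 0.74–0.94 without and 2.6–4.5 with advanced findings. If *R* is instead read directly as a ratio to the general population, c = (1 − fR)/(1 − f). This runs from 0.91/0.97 = 0.94 to 0.57/0.914 = 0.62, and the share of CRCs is fR = 9% to 43%.

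**Step 3: the coarser split.** Clear versus not clear puts small adenomas together with advanced ones, so the contrast is weaker. Take *f* = 30%–50% (adenoma recurrence within 3 years, section 2.2.1) and *R* = 1.5–3, which is assumed outright. The same formula gives 0.50–0.87 for clear and 1.2–1.9 for not clear.

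**Step 4: the data available.** The updated sample size text in section 2.8 gives about 120, 170 and 50 CRCs, read here as low, intermediate and high risk. That is 340, with 195 more expected. Appendix 1.0 lists 11,944 intermediate-risk patients, of whom 7,046 had at least one follow-up and 3,773 (32%) at least two. Only CRCs after a surveillance exam bear on stopping. Even if all 50 high-risk CRCs did, 8%–32% of them is 4 to 16 events.

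**The case against.** The strongest reply is that this is a missing cross-reference and not a faulty analysis. Section 2.9.3 describes one sequence, from description through regression to multistate models, and begins it with findings at the last exam. It says the steps proceed as in the preceding sections, whose regressions include size and multiplicity of polyps at the last examination. Question 5 and section 2.9.2 identify, from follow-up results, who can stop after one further exam. Question 6b is itself posed by number of exams. Events are few, so finer cells may not be estimable.

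Much of this stands, and it rules out several stronger readings that a reader might infer.

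- *The plan ignores what the exams found.* It does not: CRC rates by findings at the last exam are planned, and section 2.9.2 uses follow-up findings.
- *All patients are averaged together.* Stopping is examined within baseline subgroups.
- *The pooled risk fits nobody.* At a 3% share, a pooled 1.0 is close to the 0.89–0.94 of patients without advanced findings.
- *The study cannot answer its own question about negative exams.* Negative exams appear only in the background. No listed research question mentions them.

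The objection does not close the gap. The Cox model that section 2.9.3 goes on to specify names only the visit count and baseline characteristics, and the stopping sentence does not refer back to the findings-based rates. The regression in section 2.9.2 has adenoma findings as its outcome, whereas section 2.3.1 says questions 6–8 focus on long-term CRC incidence.

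**Conclusion.** The point holds in a limited form. The CRC stopping analysis for question 6d is defined by exam count within baseline subgroups, and the planned CRC rates by findings at the last exam are not carried into it. A reassuring pooled risk would then also cover a small group with advanced surveillance findings.

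Under the borrowed inputs, that group's risk would be 2.6 to 4.5 times that of the general population when the pooled ratio is 1.0. Patients without such findings would be at 0.74 to 0.94, so the misfit falls mainly on the smaller group. These figures are illustrative. They rest on carrying baseline relative risks over to surveillance findings and on advanced-finding shares from other studies. The textual gap does not depend on them. The change is a cheap improvement and does not imply that the analysis as a whole is invalid.

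**What to change.** In section 2.9.3, and in the matching sentence of section 2.3.1, state that question 6d will be answered from CRC risk by exam number combined with the finding at the preceding exam. Wording along these lines would do:

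> For question 6d, absolute CRC risk and its ratio to the general population will be estimated after each surveillance exam, by exam number and by the finding at that exam (no adenoma v any adenoma). Finer adenoma classes and the number of consecutive clear exams will be used where CRC numbers allow. In the Cox model this state will be time-varying, updated at each exam, alongside the number of visits.

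Clear versus not clear is the main split because it is the most likely to be estimable. It does not isolate advanced findings, so the plan should say in advance when the finer classes will be reported, for example by a minimum number of CRCs per cell. No clinical threshold for stopping needs to be set.

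The cost is a wording change and one recoded variable from endoscopy and pathology data already in the study database. The downside is fewer CRCs per cell and wider intervals, mainly in the high-risk group.

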# 2.7 Outcome measures

- Colorectal cancer diagnosed symptomatically or at follow-up colonoscopy.
- Multiple or advanced adenomas detected at follow-up colonoscopy. Advanced adenomas are defined as adenomas larger than 1 cm, with severe dysplasia or with tubulovillous or villous histology.
- The subsite of adenomas which will inform about whether or not flexible sigmoidoscopy is adequate for surveillance.
- For the psychological impact analysis: anxiety, bowel cancer worry, number of GP visits and bowel symptoms.
- For the economic analyses: cost per cancer avoided and cost per life year saved

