# 2.9 Statistical analysis

#### 2.9.1. Baseline and first follow-up screen analyses

a. Simple analysis of rates of events since last examination

In the first instance we will use simple descriptive statistics to summarise findings at first follow-up colonoscopy in relation to time since baseline examination, and consider the detection rates of advanced adenomas at subsequent examination stratified by findings at baseline examination, interval since baseline examination, age and sex. There is particular a priori interest in comparing intervals of less than 4 years (i.e. roughly 3 years) with intervals of 4-6 years (roughly 5 years). The stratification by baseline findings is particularly important, as there is likely to be heterogeneity, which in turn should inform policy.

We will be dealing with the detection of adenomas in the large bowel at first follow-up examination. These will be relatively common premalignant conditions (in a population all of whom have already had at least one such lesion). Practice in terms of interval to follow-up examination is not standard, and we will use this variability in practice to deduce the relative effects of different policies. If there are larger prevalences observed with longer intervals, this would suggest a suitable interval at which a sufficiently large harvest of polyps will result to render the practice effective and economical. On the other hand, a constant detection rate with time since last examination might lead us to suspect that de novo lesions were relatively rare and the constant harvest is of lesions missed at the baseline examination.

The above approach is attractive because of its simple, empirical nature. We would, however, wish to quantify our qualitative conclusions, and to extrapolate to intervals other than those for which we have data, for example to almost immediately after baseline examination, in relation to the issue of missed lesions. For this, more formal statistical analyses would be necessary.

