In order to examine appropriate surveillance interval lengths, we will analyse the yield of advanced adenomas and CRC at surveillance visits by interval in patients who attended follow-up after baseline. In the high-risk group we will also examine the effect of a short vs a longer surveillance interval (one year as recommended vs longer than one year) on long-term CRC incidence. In order to investigate this, we will create crude groupings based on the interval to first follow-up exam and the incidence of CRC between groups will be compared.

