#### Clarifications

#### a) Study Datasets (see Protocol sections 2.3 and 2.8).

The Intermediate Adenoma study was designed to create one study database from a combination of the screening and hospital datasets. However, the hospital dataset alone provided sufficient power to conduct the analyses, allowing us to reserve the screening dataset for validation of the analyses in the hospital dataset.

	Patients with intermediate adenomas (n)		
Sample size required for analysis:	Baseline	≥ 1 follow-up colonoscopy	≥ 2 follow-up colonoscopies
Endpoint	Colorectal cancer	Advanced adenoma	Advanced adenoma
Total number of endpoints required	60	198	36
Total number of patients required	10,000	6,600	1,200
Actual number of patients obtained from UK hospital databases (endoscopy / pathology data). Data to end 2014 (the Intermediate Adenoma study cohort)	11,944	7,046	3,773

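### Sections 2.9.1 and 2.9.3 do not say how a CRC diagnosed before the first follow-up examination enters the interval comparisons, so the absolute excess at longer intervals is understated

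*Combined protocol and SAP*

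**What the plan says.** Two parts of the plan compare intervals by what is found at an examination. Section 2.9.1(a) will "consider the detection rates of advanced adenomas at subsequent examination stratified by findings at baseline examination, interval since baseline examination, age and sex", with under 4 years against 4-6 years as the contrast of prior interest. Section 2.9.3 will examine interval length through yield: "we will analyse the yield of advanced adenomas and CRC at surveillance visits by interval in patients who attended follow-up after baseline".

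For high-risk patients, section 2.9.3 adds a comparison of long-term CRC incidence ("one year as recommended vs longer than one year"), for which "we will create crude groupings based on the interval to first follow-up exam and the incidence of CRC between groups will be compared".

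Cancers outside surveillance visits are covered elsewhere. Section 2.7 includes as an outcome "Colorectal cancer diagnosed symptomatically or at follow-up colonoscopy". Section 2.9.1(c) models progression to CRC between examinations. Section 2.9.3 plans CRC rates by time since last examination, Kaplan-Meier curves, Cox models with number of visits as a time-varying covariate, and a trade-off between polyp harvest and the "expected number of cancers occurring before the subsequent examination".

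No section says which interval group holds a patient whose CRC is diagnosed before the first follow-up examination, whether a colonoscopy prompted by symptoms counts as follow-up, or when the clock starts in the high-risk comparison. Appendix 1.0(b) refers back to section 2.9 and adds no rule.

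**The concern.** Question 8 in section 2.3.1 asks for intervals that do not allow too many interval cancers. By definition these arise before the next examination, so a comparison restricted to attenders and to findings at surveillance visits cannot contain them unless a rule puts them there. A longer interval leaves more time for such cancers, so the omission removes more events from the longer group.

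The high-risk comparison has a related problem. The groups are defined by an event after baseline. A patient can join the five-year group only by reaching five years without a CRC diagnosis, and counting those years as time at risk lowers that group's rate whether or not the interval matters. Section 2.9.3 makes the number of visits time-varying but says nothing equivalent about interval length.

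The study hypothesis (section 2.2, surveillance following adenoma removal) is that less surveillance can suffice. An error that flatters longer intervals therefore runs in the unconservative direction.

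**Working it through.** **Inputs.** From section 2.8: expected yield 3% at 2-4 years and 5% at 4-6 years; CRC rate after endoscopy 2.5 to 5 per 1,000 a year. Follow-up: 6 years in the current data (section 2.8, updated calculations) and about 10 years (section 2.3.3).

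**The plan's own figures.** Section 2.8 asks for 4,400 patients to separate 5% from 3% with 90% power, two-sided 5%. The usual two-proportion formula with equal groups gives 2,016 per group, 4,032 in all (4,230 with continuity correction). With 2,200 per group the power is 92.3%, so the stated figure is conservative, and nothing below depends on it. The person-years agree: 60/0.005 = 12,000 and 60/0.0025 = 24,000.

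**Step 1: cancers left out of visit yield.** Assume a constant CRC rate r and examinations at exactly 3 and 5 years. CRC before the examination is c = 1 - exp(-r × t). Yield including these cancers is c + (1 - c) × visit yield.

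| r per 1,000 a year | c at 3 y | c at 5 y | including them, 3 y vs 5 y | difference | ratio |
|---|---|---|---|---|---|
| left out | – | – | 3.0% vs 5.0% | 2.0 points | 1.67 |
| 2.5 | 0.75% | 1.24% | 3.7% vs 6.2% | 2.5 points | 1.66 |
| 5 | 1.49% | 2.47% | 4.4% vs 7.3% | 2.9 points | 1.65 |

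Leaving them out hides about 0.5 points at 2.5 per 1,000 and 0.9 points at 5 per 1,000. The ratio barely moves.

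**Step 2: if the diagnostic colonoscopy were coded as first follow-up.** A cancer found on symptoms at year 2 or 3, in a patient due at year 5, would then count in the under-4-years group. Simulation of 4 million patients: half due at a time uniform on 2-4 years and half on 4-6 years, advanced lesions arising at 0.0102 a year, all CRCs before the examination symptomatic.

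- 2.5 per 1,000: by planned interval 3.7% vs 6.1% (ratio 1.64); such cancers dropped, 3.0% vs 5.0%; diagnostic examination counted as follow-up, 4.7% vs 5.2% (ratio 1.11).
- 5 per 1,000: by planned interval 4.4% vs 7.3%; diagnostic examination counted, 6.3% vs 5.4% (ratio 0.86, a reversal).

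**Step 3: guaranteed CRC-free time in the high-risk comparison.** Set the true effect of interval to nil. Start the clock at baseline, leave CRCs before the first examination unassigned, and follow to T years. For an examination at t, the probability of an observed event is p = 1 - exp(-r × (T - t)), person-time is t + p/r, and the rate is their quotient. With r = 0.0025 and T = 10:

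- t = 1: p = 0.02225, person-time 9.900 years, rate 2.25 per 1,000.
- t = 5: p = 0.01242, person-time 9.969 years, rate 1.25 per 1,000; ratio to t = 1 is 0.55.

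The ratios for t = 2 and 3 are 0.89 and 0.78. The quick approximation (T - t)/(T - 1) gives 8/9, 7/9 and 5/9. With T = 6 the ratios for 2, 3 and 5 years are 0.80, 0.60 and 0.20. They hardly depend on r.

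**The case against.** The strongest reply is that the plan already deals with these cancers. Section 2.3.1 says that questions 6 to 8 rest on long-term CRC incidence after baseline, so visit yield is only one input to question 8. Section 2.9.1(c) estimates progression to CRC between examinations and treats the result as its most formal criterion for choosing intervals. Section 2.9.3 sets harvest against cancers before the next examination. This stands: a reader might infer that the plan overlooks interval cancers, and the documents do not support that. What is missing is the link from those analyses to the interval groups.

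Three further points on that side stand.

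- Appendix 1.0(a) shows 11,944 - 7,046 = 4,898 intermediate-risk patients (41%) with no follow-up colonoscopy. It is tempting to read this as the size of the bias. It counts people without examinations, not cancers lost, and question 6a and the Kaplan-Meier analysis cover those without surveillance.
- Counting a symptom-led colonoscopy as follow-up is a strained reading. Section 2.9.3 speaks of surveillance visits, and section 2.7 separates symptomatic diagnosis from diagnosis at follow-up colonoscopy. The outcomes named in section 2.9.1 are also adenomas.
- The reversal in step 2 needs that reading and 5 CRCs per 1,000 a year. If the count of 170 in section 2.8 is the intermediate-risk group, the observed rate is about 170/(11,944 × 6) = 2.4 per 1,000 a year, half as high, and that count is not limited to symptomatic cancers before a first examination.

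Planned intervals are not listed among the recorded data, so the contrast by planned interval is a benchmark and not an analysis the study could run. Early examinations may also reflect clinical judgement of higher risk, as section 2.3.1 notes, so any comparison by examination time needs care. Neither point supplies the missing rule.

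**Conclusion.** The point holds as a gap in sections 2.9.1 and 2.9.3. The yield comparison understates the absolute excess at the longer interval by about 0.5 points at 2.5 CRCs per 1,000 a year and 0.9 at 5, with the ratio almost unchanged. A larger distortion is possible only if diagnostic colonoscopies are coded as first follow-up, which the text does not expressly exclude.

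In the high-risk comparison, a clock started at baseline would give a false rate ratio of about 0.89, 0.78 and 0.55 for first examinations at 2, 3 and 5 years against one year over 10 years. If the clock started at the first examination instead, this artefact would go, but the cancers before that examination would then not be counted at all.

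These sizes assume a constant CRC rate, examinations at fixed times in steps 1 and 3, no competing deaths and, in step 3, no true effect of interval. A reader might conclude that the study will generally make long intervals look safe. The documents do not support that: when the cancers are simply left out, the longer interval still shows the higher yield (5.0% vs 3.0%), and separate analyses of these cancers are planned.

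**What to change.** 1. State in sections 2.9.1 and 2.9.3 that an examination leading to a CRC diagnosis on symptoms is not a surveillance visit and does not define the interval to first follow-up.
2. Beside the visit yield at time t, report for each risk group the cumulative incidence of CRC from baseline to t among patients not yet re-examined. Censor at the first surveillance examination, and include never-examined patients through registry data. Base interval conclusions on both components, and note that examination timing may be informative.
3. For the high-risk comparison, state the time origin and use either a landmark or time to first examination as a time-varying exposure from baseline. With a time-varying exposure, CRCs before the examination count as events in not-yet-examined time.

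Examination dates and national cancer registrations are already in the All Adenomas study database (Appendix 1.0(a)). The cost is some wording, one further analysis and slightly more complex two-component reporting. The intermediate-risk analyses already reported need not be reopened; the rules would apply to the new risk groups and to the re-examination with longer follow-up.
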